### **3.3 Inclusion of Women and Minorities**

Both men and women of all races and ethnic groups are eligible for this trial.

## **4. SUBJECT REGISTRATION**

### **4.1 General Guidelines for DF/HCC Institutions**

Institutions will register eligible participants in the Clinical Trials Management System (CTMS) OnCore. Registrations must occur prior to the initiation of protocol therapy. Any participant not registered to the protocol before protocol therapy begins will be considered ineligible and registration will be denied.

An investigator will confirm eligibility criteria and a member of the study team will complete the protocol-specific eligibility checklist.

Following registration, participants may begin protocol therapy. Issues that would cause treatment delays should be discussed with the Overall Principal Investigator (PI). If a participant does not receive protocol therapy following registration, the participant's registration on the study must be canceled. Registration cancellations must be made in OnCore as soon as possible.

#### **4.2 Registration Process for DF/HCC Institutions**

DF/HCC Standard Operating Procedure for Human Subject Research Titled *Subject Protocol Registration* (SOP #: REGIST-101) must be followed.

#### **4.3 General Guidelines for Other Investigative Sites**

Eligible participants will be entered on study centrally at the DFCI by the Project Manager. All sites should call the Project Manager to verify treatment availability.

Following registration, participants should begin protocol therapy within 5 days. Issues that would cause treatment delays should be discussed with the Overall PI. If a participant does not receive protocol therapy following registration, the participant's registration on the study must be canceled. The Project Manager should be notified of cancellations as soon as possible.

#### **4.4 Registration Process for Other Investigative Sites**

To register a participant, the following documents should be completed by the research nurse or data manager and emailed/faxed to the Project Manager:

- Informed consent
- HIPAA authorization form (if not included in consent form).
- Medical History
- Diagnosis and staging assessment
- Physical Examination including review of medications (over-the-counter or prescribed) and side effects the subject is experiencing
- Vital signs (including temperature, heart rate, blood pressure, weight, height and oxygen saturation) and ECOG performance status
- ECG
- Laboratory Testing
- Documentation of at least one prior anti-cancer therapy
- Eligibility Checklist

The research nurse or data manager at the participating site will then e-mail the Project Manager to verify eligibility. To complete the registration process, the Project Manager will follow DF/HCC Standard Operating Procedure for Human Subject Research Titled *Subject Protocol Registration* (SOP #: REGIST-101) and register the participant on the protocol. The Project

Manager will fax or e-mail the participant study number, and if applicable the dose treatment level, to the participating site. The Project Manager will also call the research nurse or data manager at the participating site and verbally confirm registration.

## **5. TREATMENT PLAN**

### **5.1 Pre-medication and Hydration**

Prophylactic use of anti-emetic, anti-nausea, and anti-diarrheal medications are encouraged and may be used prior to first dose of TAK-228, and as needed throughout the study prior to each dosing and as clinically indicated per standard practice. When selecting an anti-emetic agent, drugs that do not have an effect on the QT interval are preferred. Subjects should be encouraged to drink at least 18-24 oz of liquids a day.

**5.1.1 Antiemetic Recommendations:** These guidelines are strongly recommended to prevent treatment associated nausea but will not constitute deviations if not followed.

Cycle 1 Day 1: IV Palonosetron (Aloxi) 0.25 mg infusion administered in clinic prior to first TAK-228 administration (dosing of study drug may be done outside of clinic).

- Recommend prescribing prochlorperazine 10 mg orally as needed every 6 hours and lorazepam 0.5 mg as needed every 6 hours for nausea following study drug administration. Encourage the patient to alternate between the two anti-emetics if nausea persists.

Cycle 1 Day 8 (and subsequent dosing days): If first dose of TAK-228 was tolerated well with IV palonosetron and as needed anti-emetics, subsequent dosing will include only oral antiemetic prophylaxis prior to TAK-228 dosing.

- Recommend prescribing ondansetron 8mg and instruct patient to take ondansetron orally at least 30-60 minutes prior to TAK-228 dosing.
- If nausea after TAK-228 dosing persists, recommend providing patient with prochlorperazine 10 mg every 6 hours and lorazepam 0.5 mg every 4-6 hours as needed. Alternating between the two anti-emetics is recommended if nausea persists.

### **5.2 TAK-228 Administration**

Eligible subjects will be registered and will receive treatment with TAK-228 at a dose of 30 mg by mouth weekly on Day 1, Day 8, Day 15 and Day 22. Each cycle will be 4 weeks (28 days) in duration.

TAK-228 capsules should not be opened, dissolved or crushed. TAK-228 capsules should be swallowed whole on an empty stomach. Subjects should be instructed to refrain from eating and drinking (except for water and prescribed medications) for 2 hours before and 1 hour after each dose. If the subject chews or sucks the capsules by error, the subject should drink a large glass

of water (~8 oz). Direct contact with the powder in TAK-228 capsules with skin or mucous membranes should be avoided. If such contact occurs, the subject should wash thoroughly with water.

Subjects should be instructed to take their study medication at approximately the same time on each scheduled dosing day and not to take more than the prescribed dose at any time. If a subject does not take his or her TAK-228 dose within the time frame specified ( $\pm$  24 hours of the QW scheduled dosing time), then the dose should be skipped and considered a missed dose. Subjects should record any missed doses in their diary and resume drug administration at the next scheduled time with the prescribed dosage. Under no circumstance should a subject repeat a dose or double-up doses. The subject will be asked to bring their diary and pill bottle to their clinic visits.

If severe emesis or mucositis prevents the subject from taking scheduled doses, that dose will be skipped. If emesis occurs after study medication ingestion, the dose will not be re-administered and subjects should resume dosing at the next scheduled time with the prescribed dosage. Subjects should record the occurrence of the emesis in their dosing diaries. Under no circumstance should a subject repeat a dose or double-up doses.

#### TAK-228 Administration

Drug	Dose	Route 	Schedule	Cycle Length 
TAK-228	30 mg (six 5 mg capsules)	Orally	Day 1, Day 8, Day 15 and Day 22	4 weeks/28 days)
 Capsules should be taken whole with water. No food should be consumed within 2 hours before and one hour after the dose. Capsules should not be chewed, crushed or dissolved. If vomited, the capsules should not be retaken.  A window of $\pm$ 3 days may be applied to all study visits to accommodate observed holidays, inclement weather, scheduling conflicts etc. Date and time of each drug administration should be clearly documented in subject's chart and electronic case report forms (eCRFs).				

#### 5.2.1 Prior to Cycle 1 Day 1, the following parameters must be met:

- ANC  $\geq$  1500/mm^3.
- Platelet count  $\geq$  100,000/mm^3.
- Hemoglobin  $\geq$  9 g/dL (transfusions allowed).

#### 5.2.2 Subsequent cycles

No specific parameters to be met for subsequent cycles.

#### 5.3 Subject Evaluations

Subjects will be evaluated clinically every week for Cycle 1, every 2 weeks for Cycles 2-3, and then every 4 weeks for subsequent cycles. On the days that a subject is seen in clinic, subjects are not required to physically dose in clinic. There is no in-clinic dosing requirement.

Subjects will undergo disease assessments with imaging every 8 weeks relative to the C1D1 visit and continue on study therapy until radiographic progression, unacceptable toxicity or withdrawal.

Subjects that do not have archived tissue from the previous 18 months available will undergo one mandatory biopsy at screening. The pretreatment biopsy must occur within 28-days prior to initiation of therapy. In subjects who have an objective disease response as per RECIST version 1.1 and then subsequently progress, a second biopsy at time of progression will be mandatory if feasible and safe. Subjects should continue study treatment until the day prior to the progression biopsy. Progression biopsy must occur within 28-days of determination of disease progression.

## **5.4 Concomitant Medications**

All prescription and over-the-counter medications, including influenza vaccines, taken by a subject within 30 days before the first study drug administration will be recorded on the designated CRF.

### **5.4.1 Allowed Concomitant Medications**

- Histamine H2 receptor antagonists may be allowed, if needed provided that the histamine H2 receptor antagonist is not taken within 12 hours before and within 6 hours after study drug administration. Subjects receiving histamine H2 receptor antagonists before enrollment must stop using these medications for at least 24 hours before their first dose of study drug. Examples of histamine H2 receptor antagonists include ranitidine, famotidine, and nizatidine. Cimetidine, a moderate cytochrome P450 (CYP)1A2 inhibitor, is not recommended as a first choice H2 receptor antagonist.
- Low molecular weight heparin (LMWH) is allowed
- Palliative XRT to pre-existing lesion is allowed
- Other medications considered necessary for the subject's safety and well-being may be given at the discretion of the site investigator. Any concomitant medications added or discontinued during the study should be recorded on the Case Report Forms (CRF).
- Neutralizing antacid preparations (acid neutralizers) and calcium supplements are not permitted during Cycle 1 on study drug administration days, but may be taken as needed on non-TAK-228 administration days. However, for all other cycles of the study administration of neutralizing antacids and calcium preparations is permitted except from 4 hours before until 2 hours after TAK-228 administration. Some anti-gas preparations may also have antacid properties, and should also not be permitted from 4 hours before until 2 hours after study drug administration

### **5.4.2 Prohibited Concomitant Medications**

The following medications/therapies are prohibited during the study:

- Other investigational agents or mTOR inhibitors.
- Other anticancer therapies including chemotherapy, immunotherapy, radioimmunotherapy, targeted agents, radiation or surgery (subjects can have palliative radiation or surgery in the study for pre-existing lesions).

- Systemic corticosteroids (either IV or oral steroids, excluding inhalers or intraarticular, intraocular steroids) unless necessary for treatment of TAK-228 related AE (such as, rash).
- Anti-epileptic drugs for subjects with treated brain metastasis.
- Concomitant administration of any PPI is not permitted during the study. Subjects receiving PPI therapy before enrollment must stop using the PPI for 7 days before their first dose of study drugs. Examples of PPIs include omeprazole, esomeprazole, pantoprazole, lansoprazole, and rabeprazole.
- Strong CYP1A2 inhibitors and CYP inducers should be administered with caution, at the discretion of the investigator (see Appendix C). Alternative treatments, if available, should be considered.
- Use of concomitant medications that are known to prolong the QTc interval is strongly discouraged. If use is medically indicated, caution is advised with increased EKG for QTc monitoring.

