## **9. CRITERIA FOR DISEASE EVALUATION**

For the purposes of this study, subjects should be re-evaluated for response every 8 weeks. Response and progression will be evaluated in this study using the new international criteria proposed by the Response Evaluation Criteria in Solid Tumors (RECIST) guideline (version 1.1) (23). Changes in the largest diameter (unidimensional measurement) of the tumor lesions and the shortest diameter in the case of malignant lymph nodes are used in the RECIST criteria.

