## 9.2 Disease Parameters

Measurable disease. Measurable lesions are defined as those that can be accurately measured in at least one dimension (longest diameter to be recorded) as  $\geq 20$  mm by chest x-ray or  $\geq 10$  mm with CT scan, MRI, or calipers by clinical exam. All tumor measurements must be recorded in millimeters (or decimal fractions of centimeters).

**NOTE:** Tumor lesions that are situated in a previously irradiated area might or might not be considered measurable.

Malignant lymph nodes. To be considered pathologically enlarged and measurable, a lymph node must be  $\geq 15$  mm in short axis when assessed by CT scan (CT scan slice thickness recommended to be no greater than 5 mm). At baseline and in follow-up, only the short axis will be measured and followed.

Non-measurable disease. All other lesions (or sites of disease), including small lesions (longest diameter  $< 10$  mm or pathological lymph nodes with  $\geq 10$  to  $< 15$  mm short axis), are considered non-measurable disease. Bone lesions, leptomeningeal disease, ascites, pleural/pericardial effusions, lymphangitis cutis/pulmonitis, inflammatory breast disease, abdominal masses (not followed by CT or MRI), and cystic lesions are all considered non-measurable.

**NOTE:** Cystic lesions that meet the criteria for radiographically defined simple cysts should not be considered as malignant lesions (neither measurable nor non-measurable) since they are, by definition, simple cysts.

'Cystic lesions' thought to represent cystic metastases can be considered as measurable lesions, if they meet the definition of measurability described above. However, if non-cystic lesions are present in the same subject, these are preferred for selection as target lesions.

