Target lesions. All measurable lesions up to a maximum of 2 lesions per organ and 5 lesions in total, representative of all involved organs, should be identified as target lesions and recorded and measured at baseline. Target lesions should be selected on the basis of their size (lesions with the longest diameter), be representative of all involved organs, but in addition should be those that lend themselves to reproducible repeated measurements. It may be the case that, on occasion, the largest lesion does not lend itself to reproducible measurement in which circumstance the next largest lesion which can be measured reproducibly should be selected. A sum of the diameters (longest for non-nodal lesions, short axis for nodal lesions) for all target lesions will be calculated and reported as the baseline sum diameters. If lymph nodes are to be included in the sum, then only the short axis is added into the sum. The baseline sum diameters will be used as reference to further characterize any objective tumor regression in the measurable dimension of the disease.

Non-target lesions. All other lesions (or sites of disease) including any measurable lesions over and above the 5 target lesions should be identified as non-target lesions and should also be recorded at baseline. Measurements of these lesions are not required, but the presence, absence, or in rare cases unequivocal progression of each should be noted throughout follow up.

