### 9.4 Response Criteria

#### 9.4.1 Evaluation of Target Lesions

Complete Response (CR): Disappearance of all target lesions. Any pathological lymph nodes (whether target or non-target) must have reduction in short axis to  $< 10$  mm.

Partial Response (PR): At least a 30% decrease in the sum of the diameters of target lesions, taking as reference the baseline sum diameters.

Progressive Disease (PD): At least a 20% increase in the sum of the diameters of target lesions, taking as reference the smallest sum on study (this includes the baseline sum if that is the smallest on study). In addition to the relative increase of 20%, the sum must also demonstrate an

absolute increase of at least 5 mm. (Note: the appearance of one or more new lesions is also considered progressions).

Stable Disease (SD): Neither sufficient shrinkage to qualify for PR nor sufficient increase to qualify for PD, taking as reference the smallest sum diameters while on study.

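### On-study palliative radiation or surgery may be given to a target lesion, and no rule stops the resulting shrinkage from being counted as an objective response

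*Combined protocol and SAP*

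**What the plan says.** **Permission.** Section 5.4.1 lists, among allowed measures, "Palliative XRT to pre-existing lesion is allowed". Section 5.4.2 prohibits other anticancer treatment, including radiation and surgery, but with the exception that "subjects can have palliative radiation or surgery in the study for pre-existing lesions". Neither section separates target from non-target lesions. Targets are chosen at baseline (section 9.2: "All measurable lesions up to a maximum of 2 lesions per organ and 5 lesions in total"), so every target is a pre-existing lesion.

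**Response.** Section 9.4.1 defines partial response as "At least a 30% decrease in the sum of the diameters of target lesions, taking as reference the baseline sum diameters", with no condition on what caused the decrease. Section 12.2.1 makes confirmed complete or partial response by central review the primary endpoint. It counts designations from first dose until documented progression or the end of trial therapy, whichever is earlier. Table 17 asks for confirmation at 4 weeks or more. Section 5.5 does not list local therapy among the reasons for stopping treatment.

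**Handling of treated lesions.** The only sentence on irradiated lesions is a note in section 9.2: "Tumor lesions that are situated in a previously irradiated area might or might not be considered measurable". Section 9 adopts RECIST 1.1 by reference ("Response and progression will be evaluated in this study using the new international criteria"), and section 9.4.6 assigns assessment to central radiology review. The evaluable population (12.4) and the response analysis (12.4.1) do not mention local therapy.

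**Decision rule.** Section 12.3 continues to stage 2 on 1 or more responses among 19 evaluable subjects. The drug is worth further study if 5 or more of 38 respond.

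**The concern.** Read together, these sections let a target lesion be irradiated or removed while the subject stays on TAK-228 and stays in the response window. The lesion's shrinkage then enters the target sum like any other. Confirmation does not filter this out, because a resected lesion is still absent 4 weeks later. The section 9.2 note concerns measurability, leaves its own question open and does not cover surgery.

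The trial has one arm, so no control group would show the same artefact. The threshold is five responses and the futility rule needs one, so a single case credited in error could carry the trial past stage 1 or turn four responses into five. If a rule were written only after such a case had appeared, the choice would look driven by the result.

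**Working it through.** **1. The plan's own figures.** Inputs from section 12.3: 19 evaluable in stage 1, 38 in total, continue if at least 1 response, success if at least 5, null rate 0.05, target rate 0.20.

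- P(stop at stage 1) = (1 − p)^19, which is 0.95^19 = 0.377 under the null and 0.80^19 = 0.014 under the alternative.
- P(success) = Σ over x ≥ 1 of P(Bin(19, p) = x) × P(Bin(19, p) ≥ 5 − x), which is 0.039 at p = 0.05 and 0.897 at p = 0.20.

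These agree with the stated 38%, 1.4%, 0.04 and 90%. The design arithmetic is sound.

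**2. What it takes for local therapy to produce a partial response.** With the other targets unchanged, the condition is (treated lesion's share of the baseline sum) × (fractional shrinkage) ≥ 0.30. The share must be at least 30% if the lesion is resected (shrinkage 1), or at least 60% if its diameter is halved (0.30 / 0.5).

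Example with assumed targets of 40, 30 and 30 mm (sum 100 mm): resecting the 40 mm lesion leaves 60 mm, a 40% fall, which meets the definition although the untreated targets have not changed. Halving the same lesion leaves 80 mm, a 20% fall, which does not.

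**3. Effect of one false response at a true rate of 5% (illustration: the event is assumed to happen).**

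- In a stage 1 subject, on record at the interim: the stage 1 rule is met automatically, and success needs 4 or more true responses among the other 37. P(Bin(37, 0.05) ≥ 4) = 0.112.
- In a stage 1 subject, arising after the interim: at least 1 of the other 18 must respond first. Σ over x ≥ 1 of P(Bin(18, 0.05) = x) × P(Bin(19, 0.05) ≥ 4 − x) = 0.107.
- In a stage 2 subject: Σ over x ≥ 1 of P(Bin(19, 0.05) = x) × P(Bin(18, 0.05) ≥ 4 − x) = 0.108. This is joint with passing stage 1, which has probability 1 − 0.377 = 0.623.

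All three are about 0.11, against 0.039 as designed.

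**4. Effect of a rate (assumed, because the document gives none).** If a fraction q of true non-responders become false responders, the apparent rate is 0.05 + 0.95q.

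| q | Apparent rate | P(positive conclusion) |
|---|---|---|
| 0 | 0.0500 | 0.039 |
| 0.25% | 0.0524 | 0.046 |
| 0.5% | 0.0548 | 0.054 |
| 1% | 0.0595 | 0.072 |

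The 0.05 limit is reached near q = 0.38%. That figure shows how little slack lies between 0.039 and 0.05. It says nothing about how often the event occurs.

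**The case against.** The strongest reply is that the rules include RECIST 1.1 as applied by central review, and neither that guideline nor any central-review instructions are in the document. A central reader might call a treated target not evaluable. A reader might infer from the written definitions that such a fall would necessarily be counted, but the document does not support that: it is silent on the point. What stands is that the fall *could* count, and that the primary endpoint should not rest on an unstated choice.

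The chain of events is also long. The palliated lesion must be a measurable target (bone lesions are classed as non-measurable in section 9.2) and must hold a large share of the sum. There must be no progression elsewhere. The subject must stay on drug, although section 5.5 lets the investigator stop treatment on judgement. The fall must then be confirmed. This stands, and it is why the event is probably uncommon.

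The error rates are not evidence about this trial. The 0.11 is what any single misclassified response, from any cause, would do to a threshold of 5 in 38, and the grid of rates has no source in the document. That also stands, so the figures are illustration only.

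A reader might go further and ask for the progression rule to be rewritten, since section 9.4.1 measures progression from the smallest sum on study and local therapy lowers that sum. The case is weak. PFS is secondary and summarised descriptively (section 12.4.2). In the example, halving the 40 mm lesion lowers the progression threshold from 120 to 96 mm (80 × 1.2), which brings progression earlier and does not favour the drug. A sum restricted to untreated targets would rewrite the response criteria. It would also call progression after 12 mm of untreated growth (60 to 72 mm) instead of 16 mm (80 to 96 mm).

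**Conclusion.** The gap is real and worth closing. Sections 5.4.1 and 5.4.2 permit local therapy to targets, section 9.4.1 sets no condition on the cause of shrinkage, section 12.2.1 does not close the window at local therapy, and nothing else in the document prevents the shrinkage from being credited to TAK-228.

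Its size is conditional. If one such false response occurs at a true rate of 5%, the chance of a positive conclusion rises from 0.039 to about 0.11. The document gives no frequency, so inflation of the type I error above 0.05 is possible but not shown, and it should not be reported as a defect of the design figures, which reproduce. Confidence is moderate because the guideline and any central-review instructions cannot be checked here. The point is confined to the response endpoint. For PFS it supports only identifying the affected subjects.

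**What to change.** Add to section 12.2.1, and give to central review:

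> After on-study radiation or surgery to a target lesion, later assessments do not count toward objective response. A response met and confirmed before the local treatment counts; otherwise the subject stays in the denominator as a non-responder.

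Then:

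- Record the date and lesion site of any on-study radiation or surgery on the CRF. The recording sentence in section 5.4.1 speaks of medications, so procedures need to be named.
- Mark these subjects on the waterfall and spider plots in section 12.4.1.
- Report the response rate without the cut as a sensitivity analysis, using the full target sum with a resected target at 0 mm and an irradiated target at its measured diameter.
- For PFS, flag and list the treated subjects and leave the smallest-sum rule in section 9.4.1 as it is.

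**Cost.** One short paragraph, two CRF details, one line to central review and one extra analysis. Permission for palliation and the sample size are unchanged. The downside is that an occasional genuine responder is lost, such as a first partial response awaiting confirmation or a later response in untreated targets. If a fraction L of responders were lost (assumed), the effective rate is 0.20 × (1 − L). Power falls from 0.897 to 0.883 at L = 2.5% (rate 0.195), 0.868 at 5% (0.19) and 0.833 at 10% (0.18). The sensitivity analysis shows how much the cut mattered. Case-by-case central reading with listed cases is a lighter alternative, but it leaves the endpoint to judgement made after the scans are seen.
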